## 2. CORE PROTOCOL

### 2.1. Rationale

Human papilloma virus (HPV) is the main cause of cervical malignancies and contributes to 90% of anal cancers, 40 % of vulvar, vaginal and penile cancers and causes in lower amounts oropharyngeal and mouth cancers (1). Up to 80% of women get infected with HPV during their lives, with the highest incidence 3 to 4 years after sexual onset (2). For men the risk of infection start shortly after sexual debut and remains high for the remainder of their life and about 30% of all HPV-related cancer occurs in men. In order to induce malignancies, persistent HPV infection is needed (3). In immunocompetent persons only 10% of the infections persist >6 months.

However, in immunocompromised patients, including transplant recipients and HIV-infected patients, chronic HPV-infection is more prevailing (4). Consequently, they have an increased risk for HPV-related complications. In healthy populations, HPV vaccination is very efficacious in preventing HPV infections. Studies showed a suboptimal immunogenicity of HPV vaccination in adult transplant patients but better immunogenicity in paediatric patients and HIV-infected patients with reasonable CD4-counts (>200 cells/mm^2 or CD4% ≥15) (5-13). However, in HIV and solid organ transplant patients, research has only been done with the bivalent and the quadrivalent vaccine, which comprises virus like particles (VLPs) of HPV types 16 and 18 and types 6, 11, 16 and 18 respectively.

In this study, the immunogenicity of the nine-valent HPV vaccine will be investigated in HIV and solid organ transplant patients, who will be recruited in the university hospitals of Leuven. This tertiary hospital is large hospital located in the center of Belgium and is a reference center where patients from all over the country are treated. Approximately 415 heart, 590 lung and 700 kidney transplant patients are followed in the hospital, of whom approximately 160, 210 and 350 are between 18 and 55 years of age, respectively. About 900 HIV patients are equally followed in the university hospital of whom 470 are between 18 and 45 years old.

The nine-valent vaccine that will be used in this study comprises 5 additional VLPs of oncogenic HPV types 31, 33, 45, 52 and 58 compared to the quadrivalent vaccine and consequently has an additional preventive benefit, as it increases the coverage of all cervical cancers from 70% to 90% (14). In clinical trials in women and men (16 to 26 years of age) as well as in girls and boys (9 to 15 years of age), the 9-valent vaccine was well tolerated and prevented infection and disease due HPV types included in the vaccine (15-17). The Gardasil®9 was licensed in the US, Canada, Australia and Europe in respectively 2014 and 2015. **Gardasil®9 is currently approved for use in persons (boys and girls) as of nine**

years of age (Belgian SPC). Currently there are no data available for men or women above 26 years of age. Nevertheless, data are available on women 24 to 46 years of age for quadrivalent Gardasil® vaccine from the FUTURE III trial. By the end of this clinical trial, data of the V503-004 study which enrolled women between 16 and 45 years of age might be available

## 2.2 Objectives and hypothesis

### 2.2.1. Primary Objective Immunogenicity:

To determine the *immunogenicity* of Gardasil®9 with respect to HPV types 6, 11, 16, 18, 31, 33, 45, 52 and 58 in adult HIV (age: 18-45 years) and transplant patients (age: 18-55 years).

**Hypothesis:** GARDASIL®9 induces in 18-45-year-old **HIV patients** (>200 CD4 T cells/mm^2) seroconversion rates for HPV 6, 11, 16, 18, 31, 33, 45, 52, and 58 at 4 weeks after Dose 3 that are similar to those induced in historical controls (healthy persons between 18 and 45 years of age. If the proposed control data are not available, immunogenicity will be compared to data from male and female healthy persons between 18 and 26 years of age and previous data from the immunogenicity of Gardasil® in HIV patients). The seroconversion rate for each of the HPV types 6, 11, 16, 18, 31, 33, 45, 52, and 58 will be tested separately.

**Hypothesis:** GARDASIL®9 induces in 18-55-year-old **solid organ transplant patients** seroconversion rates for HPV 6, 11, 16, 18, 31, 33, 45, 52, and 58 at 4 weeks after Dose 3 that are similar to those induced in historical controls (healthy persons between 18 and 45 years of age. If the proposed control data are not available, immunogenicity will be compared to data from male and female healthy persons between 18 and 26 years of age). The seroconversion rate for each of the HPV types 6, 11, 16, 18, 31, 33, 45, 52, and 58 will be tested separately.

(Seroconversion is defined as changing serostatus from seronegative at Day 1 to seropositive (antibody titer above seroconversion cut-off) by 4 weeks after Dose 3)

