- The expected seroconversion rates that were used for the sample size calculation were retrieved from published data of patients with a CD4-count of 200-350 cells/mm^2. However, 92% of the patients that are currently included have a CD4-count of  $> 350$  cells/mm^2, which makes seroconversion rates in patients with more than 350 CD4+ cells/mm^2 more applicable (1). Published seroconversion rates in these patients are 95%-99% for HPV types 6, 11 and 16 and 90% for HPV-18.
- This sample size calculation does not take in to account that patients might be seropositive to certain HPV-types at baseline and that their data will be excluded for the analysis of the seroconversion outcome of the corresponding HPV-type. Seroprevalence to different HPV-types in previous studies on the safety and immunogenicity of the quadrivalent HPV-vaccine in HIV patients ranged from 13% to 45% for the different vaccine HPV-types (1-3).
- In order to maximize the number of eligible subjects, we amend the protocol to also **include patients with a history of abnormal PAP-smears without treatment or genital warts**. We believe that this allows us to reach a total sample size of at least 100 HIV-patients. Patients who are seropositive for a given HPV-type at baseline will

still be excluded for the analysis of seroconversion of that particular type but will still be useful for the analysis of the other HPV-types. Knowing that in HIV-patients the expected seroconversion rate of HPV-18 is relatively lower than the seroconversion rates of HPV types 6, 11 and 16, maximizing the number of eligible subjects for the analysis of this type is especially beneficial in order to obtain a reasonable margin of error. Enrolling patients with history of genital warts, who are most likely seropositive to HPV types 6 or 11, still allows us to increase the number of HPV-18 seronegative patients. In addition, clinical presentation of HPV infection does not necessarily implicate seropositivity to HPV.

- **With a total sample size of n=100, a majority of whom will have no history of HPV-lesions, we expect to be able to use the data of at least 80 patients for the analysis seroconversion of each HPV type under study. Seroconversion rates of 95-99% for HPV types 6, 11 and 16 can then be estimated with a margin of error of  $\pm 4.8\%$  -  $2.2\%$ , and the anticipated seroconversion rate of 90% for HPV type 18 with a margin of error of  $\pm 6.6\%$ .**

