### **1.3. Rationale**

Human papilloma virus (HPV) is the main cause of cervical malignancies (99%) and contributes to 90% of anal cancers, 40 % of vulvar, vaginal and penile cancers and causes in lower numbers oropharyngeal and mouth cancers (1). Up to 80% of women get infected with HPV during their lives, with the highest incidence 3 to 4 years after sexual onset (2). For men the risk of infection start shortly after sexual debut and remains high for the remainder of their life and about 30% of all HPV-related cancer occurs in men. In order to induce malignancies, persistent HPV infection is needed (3). In immunocompetent persons only 10% of the infections persist >6 months.

However, in immunocompromised patients, including transplant recipients and HIV-infected patients, chronic HPV-infection is more prevailing (4). Consequently, they have an increased risk for HPV-related complications. In healthy populations, HPV vaccination is very efficacious in preventing HPV infections. Studies showed a suboptimal immunogenicity of HPV vaccination in adult transplant patients but better immunogenicity in paediatric patients and HIV-infected patients with reasonable CD4-counts (>200 cells/mm^2 or CD4% ≥15) (5-13). However, in HIV and solid organ transplant patients, only a limited number of studies has been done with the bivalent and the quadrivalent vaccine, which comprises virus like particles (VLPs) of HPV types 16 and 18 and types 6, 11, 16 and 18 respectively.

In this study, the immunogenicity of the nine-valent HPV vaccine will be investigated in HIV and solid organ transplant patients, who will be recruited in the university hospitals of Leuven.

The nine-valent vaccine that will be used in this study comprises 5 additional VLPs of oncogenic HPV types 31, 33, 45, 52 and 58 compared to the quadrivalent vaccine and consequently has an additional preventive benefit, as it increases the coverage of all cervical cancers from 70% to 90% (14). In clinical trials in women and men (16 to 26 years of age) as well as in girls and boys (9 to 15 years of age), the 9-valent vaccine was well tolerated and prevented infection and disease due HPV types included in the

vaccine (15-17). The Gardasil® was licensed in the US, Canada, Australia and Europe in respectively 2014 and 2015.

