#### 1.4. Summary of study design

This is a single-center, open-label study on safety, tolerability and immunogenicity of Gardasil® in 18 to 45 year-old HIV patients, in 18 to 55 year-old solid-organ transplant (SOT) patients.

This study will enrol 100 HIV patients with CD4+ count of >200cells/mm^2 and 170 SOT patients, all of whom have not yet received a prophylactic HPV vaccine. The 170 SOT patients will be equally divided over 3 different SOT patient groups, namely heart, lung and kidney transplant patients. Therefore the target is to include approximately 57 heart transplant patients, 57 lung transplant patients and 57 kidney transplant patients. Enrolment in a SOT subgroup will be stopped when 57 patients have been included unless recruitment cannot be achieved within one of the other SOT-patient population.

All enrolled subjects will receive a 3-dose regimen (Day 1, Month 2, and Month 6) of GARDASIL®. Serum samples will be collected on Day 1 and Month 7 for anti-HPV 6, 11, 16, 18, 31, 33, 45, 52, and 58 antibody determination. The time point for comparison of immune responses will be Month 7, or approximately 4 weeks after the administration of the third dose. The safety/tolerability profile of the vaccine will be evaluated in all subjects in the study. Safety information will be collected on Day 1 through 1 month following the third vaccination or for a total of approximately 7 months for each subject.

The immunogenicity and the safety data will be analyzed per group of patients. More specifically a separate analysis of HIV and SOT patients is planned, since it is expected that the immunosuppressive therapy of SOT patients might have a more profound effect on immunogenicity following vaccination.

This study will provide a comparison of immunogenicity of Gardasil® in immunocompromised patients, with historical controls (15, 18). The number of subjects to be enrolled in the study was determined based on the primary immunogenicity objective.

---

 GARDASIL® (Human Papillomavirus 9-valent Vaccine, Recombinant) is a registered trademark of Merck Sharp & Dohme Corp., a subsidiary of Merck & Co., Inc., Whitehouse Station, New Jersey, U.S.A

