## **2.5. Study design and duration**

### **2.5.1. Study design summary**

This is a single-center, open-label study on immunogenicity and tolerability of Gardasil®9 in 18 to 45 year-old HIV patients, in 18 to 55 year-old solid-organ transplant (SOT) patients.

This study will enrol 100 HIV patients with CD4+ count of >200cells/mm^2 and 170 SOT patients, all of whom have not yet received a prophylactic HPV vaccine. The 170 SOT patients will be equally divided over 3 different SOT patient groups, namely heart, lung and kidney transplant patients. Therefore the target is to include approximately 57 heart transplant patients, 57 lung transplant patients and 57 kidney transplant patients. Enrolment in a SOT subgroup will be stopped when 57 patients have been included unless recruitment cannot be achieved within one patient population.

All enrolled subjects will receive a 3-dose regimen (Day 1, Month 2, and Month 6) of GARDASIL®9. Serum samples will be collected on Day 1 and Month 7 for anti-HPV 6, 11, 16, 18, 31, 33, 45, 52, and 58 antibody determination. The time point for comparison of immune responses will be Month 7, or approximately 4 weeks after the administration of the third dose. The safety/tolerability profile of the vaccine will be evaluated in all subjects in the study. Safety information will be collected on Day 1 through 1 month following the third vaccination or for a total of approximately 7 months for each subject.

The immunogenicity and the safety data will be analyzed per group of patients. More specifically a separate analysis of HIV and SOT patients is planned, since it is expected that the immunosuppressive therapy of SOT patients might have a more profound effect on immunogenicity following vaccination.

This study will provide a comparison of immunogenicity of Gardasil ®9 in immunocompromised patients, with historical controls (15, 18). The number of subjects to be enrolled in the study was determined based on the primary immunogenicity objective.

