### **3.5.6 Sample Size and Power Calculations**

Based on an expected seroconversion rate of 80%, a sample size of 170 transplant patients allows to estimate the proportion of protected transplant patients with precision (95% confidence interval) of  $\pm 6\%$  (10).

Furthermore, based on an expected seroconversion rate 85-91%, a sample size of 140 HIV-patients allows to estimate the proportion of protected patients with precision (95% confidence interval) of  $\pm 6\%$  and 5% respectively (7). Based on expected differences in GMT to healthy populations, a sample size of 140 HIV-patients allows to estimate the GMTs HPV type 6, 11, 16 and 18 with a power of 0.38, 0.82, 1 and 1, respectively (7, 19).

Due to difficulties in the recruitment of HIV patients without genital warts a recalculation of the sample size was done. With a total sample size of  $n=100$ , a majority of whom will have no history of HPV-lesions, we expect to be able to use the data of at least 80 patients for the analysis seroconversion of each HPV type under study. Seroconversion rates of 95-99% for HPV types 6, 11 and 16 can then be

estimated with a margin of error of  $\pm 4.8\%$  -  $2.2\%$ , and the anticipated seroconversion rate of 90% for HPV type 18 with a margin of error of  $\pm 6.6\%$ .

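### The SOT similarity hypothesis (2.2.1) is at odds with the plan's own 80% planning value and its precision-only sizing; the SOT objective should be restated as estimation of the per-type difference from controls

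*Combined protocol and SAP*

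**What the plan says.** Section 2.2.1 gives SOT patients essentially the same hypothesis as HIV patients: seroconversion rates "at 4 weeks after Dose 3 that are similar to those induced in historical controls (healthy persons between 18 and 45 years of age". If data on that control group are not available, healthy persons aged 18 to 26 take their place. The section adds that "The seroconversion rate for each of the HPV types 6, 11, 16, 18, 31, 33, 45, 52, and 58 will be tested separately". It does not define what counts as similar.

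Other sections point the other way for SOT:

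- Section 3.5.6: "Based on an expected seroconversion rate of 80%, a sample size of 170 transplant patients" allows the plan to "estimate the proportion of protected transplant patients with precision (95% confidence interval) of" ±6%. This is the whole SOT sizing argument. It contains no power, no margin and no comparison with controls. The source cited for the 80% is a quadrivalent-vaccine study in transplant recipients.
- Section 1.3, repeated in 2.1: "Studies showed a suboptimal immunogenicity of HPV vaccination in adult transplant patients".
- Section 1.4, repeated in 2.5.1: HIV and SOT are analysed separately because "it is expected that the immunosuppressive therapy of SOT patients might have a more profound effect on immunogenicity following vaccination".
- Rationale for Amendment 1, on HIV patients with more than 350 CD4+ cells: "Published seroconversion rates in these patients are 95%-99% for HPV types 6, 11 and 16 and 90% for HPV-18". Section 3.5.6 uses the same figures for the HIV cohort.

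Section 3.5.5.1 describes seroconversion with a 95% CI and then tests for differences from historical controls with a test for binary proportions. It states no margin, no significance level for that test and no rule across the nine types. No section gives a seroconversion rate for healthy controls.

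**The concern.** A planning value of 80% and a hypothesis of similarity to healthy people are hard to hold together. The plan's own anticipated rates in HIV patients, who are also immunocompromised, are 90% to 99%. The sizing supports estimating one proportion, while the hypothesis asks for a comparison that the sizing never considered.

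Two things are at stake. First, if controls respond well, the primary SOT statement will probably be contradicted by an outcome the plan already anticipates, and the informative quantity (how large the shortfall is for each type) has no named interval. Second, if the test happens not to reject, for instance because baseline seropositivity has thinned the sample, the wording of 2.2.1 invites the reader to take non-significance as similarity.

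**Working it through.** **Inputs from the documents.** SOT planning rate 80% and N = 170 (3.5.6). Only subjects seronegative for the type at Day 1 enter the primary population (3.5.4.1). Baseline seropositivity of 13% to 45% is quoted for HIV studies (Rationale for Amendment 1); there is no SOT figure.

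**Assumptions.** Two-sided 5% level, in line with the 95% CIs. The HIV seropositivity range is borrowed for SOT, so evaluable n runs from 170 down to 170 × 0.55 = 93.5, taken as 93. The control rate is not in the documents; 90% and 95% are used because they are the plan's own figures for HIV patients (HPV 18, and the low end for HPV 6, 11 and 16).

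**Step 1: the plan's own figure.** Half-width = 1.96 × √(p(1−p)/n).
- n = 170: 1.96 × √(0.80 × 0.20/170) = 6.0%, which reproduces the stated ±6%. The interval is about 74% to 86%.
- n = 93: 1.96 × √(0.16/93) = 8.1%.

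**Step 2: probability that a difference test rejects if the true SOT rate is 80%.**

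Fixed control rate, exact binomial test. At n = 170 and a control rate of 90%, the test rejects on the low side at 144 or fewer seroconverters, and P(X ≤ 144 | 0.80) = 0.95. At n = 93 the limit is 77, and the probability is 0.79.

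Control as a sample: power = Φ[(d − 1.96·s0)/s1], where d is the difference, s0 the pooled and s1 the unpooled standard error. For 93 against 93 at 90%: s0 = √(0.85 × 0.15 × 2/93) = 0.0524 and s1 = √(0.16/93 + 0.09/93) = 0.0518, so Φ[(0.10 − 0.1026)/0.0518] = Φ(−0.05) = 0.48.

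| SOT n | Control | Control rate 90% | Control rate 95% |
|---|---|---|---|
| 170 | fixed rate | 0.95 | >0.999 |
| 170 | sample of 1000 | 0.93 | >0.999 |
| 170 | sample of 300 | 0.84 | 0.997 |
| 170 | sample of 170 | 0.74 | 0.99 |
| 93 | fixed rate | 0.79 | 0.994 |
| 93 | sample of 93 | 0.48 | 0.88 |

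Control sample sizes are assumed; the documents give none.

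**Step 3: chance of showing similarity if a margin existed.** Take a 5- or 10-point margin (both assumed) and require the Wilson 95% lower bound to exceed the fixed control rate minus the margin. With a true rate of 80%, the chance is at most 3% at a control rate of 90% and under 0.1% at 95%, for n from 93 to 170.

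**Step 4: precision of the difference.** Half-width = 1.96 × √(p1(1−p1)/n1 + p2(1−p2)/n2). Against an assumed 300 controls at 90%:
- n1 = 170: 1.96 × √(0.16/170 + 0.09/300) = 6.9%.
- n1 = 93: 1.96 × √(0.16/93 + 0.09/300) = 8.8%.

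**The case against.** A reader might infer that, on the plan's own figures, the SOT hypothesis is almost certain to be rejected, so that the result is settled in advance. The documents do not support that reading. The deciding input, the healthy-control rate, is nowhere stated. At an assumed 90% the probability falls as low as 0.48. At 85% it would be 0.22 to 0.38 against a fixed rate for n = 93 to 170, although that would place healthy people below what the plan anticipates for HIV patients.

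Further points on that side also stand:

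- The 80% is one sizing value from a quadrivalent-vaccine study. It says nothing direct about types 31, 33, 45, 52 and 58, and it may not represent each of the other four. Setting it against the HIV figures (a gap of 10 to 19 points) is not a type-by-type forecast.
- Sections 1.4 and 2.5.1 say only that immunosuppression might have a more profound effect. The word suboptimal in 1.3 is not tied to seroconversion; GMT is an endpoint too.
- Part of the remedy already exists. The objective is worded as determining immunogenicity, and 3.5.5.1 already gives a 95% CI for the rate.
- A rejection would not be worthless: section 1.3 reports no nine-valent results in SOT patients.

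What this does not remove is the mismatch itself. Nor can a difference test without a margin support similarity when it fails to reject, whatever the control rate turns out to be.

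**Conclusion.** The point holds in conditional form. The SOT hypothesis conflicts with the plan's own planning value and with its description of the transplant response. It would very probably be contradicted if healthy controls seroconvert at about 95% or more; at 90% rejection ranges from about even odds to very likely. This rests on a true SOT rate of 80%, a two-sided 5% test, a control rate taken from figures for a different population, and seropositivity borrowed from HIV studies for the lower sample size. Certainty of rejection cannot be claimed from these documents. In either case the planned analysis cannot establish the hypothesis as worded, and the sample size supports estimation. This is a worthwhile, low-cost improvement rather than a flaw that invalidates the data.

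**What to change.** - **Section 2.2.1:** replace the SOT hypothesis with an estimation objective, for example: *In SOT patients, the seroconversion rate for each vaccine type and its difference from healthy historical controls will be estimated with 95% confidence intervals; a lower rate than in controls is expected (planning value 80%).* The HIV hypothesis can be handled separately.
- **Section 3.5.5.1:** make the per-type difference with its 95% CI the primary SOT result, and state that a non-significant test will not be read as similarity.
- **Section 3.5.6:** state that ±6% is the half-width for a single proportion at n = 170 (about ±8% at n = 93), and that the difference is less precise, with the assumed control rate and size given (the illustration above yields ±6.9% and ±8.8%). Note that the 80% has no direct basis for the five added types.

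If the sponsor prefers to keep a similarity claim, the plan needs a control rate, a margin and a decision rule across the nine types, and it should explain how these fit with an expected 80%.

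**Cost:** a protocol amendment before database lock, which section 3.5 already requires when a primary hypothesis changes. No extra patients, samples or visits. The sponsor gives up a formal SOT similarity claim.

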## IMMUNOGENICITY

### 2.3. Subject inclusion criteria

To be included in the study and to receive the first study vaccination, subjects must meet all inclusion criteria. For items with an asterisk (\*), if the subject does not meet these inclusion criteria, the Day 1 visit may be rescheduled to a time when these criteria can be met.

1. Independent Ethics Committee (IEC)-approved written informed consent form (ICF) must be obtained from the subject prior to any study-related procedure (including discontinuation of prohibited medication, if applicable) as required by local law.
2. Subject (man or woman) is between the age of 18 years and 0 days and 45 years and 365 days for HIV patients, between 18 years and 0 days and 55 years and 365 days for transplant patients at time of signing the ICF.
3. Subject is able to understand and adhere to the study procedures (e.g., is not planning to relocate far from the investigational centre during the study period); is able to read, understand, and complete the vaccination diary; is able to understand the risks involved with the study; and voluntarily agrees to participate in the study by giving written informed consent.
4. \* Since the first day of their last menstrual period through Day 1, female subjects have not had sex with males or has had sex with males and used effective contraception with no failures (an example of a failure is a male condom that ruptures during sexual intercourse). Effective contraception is defined as a marketed, approved contraceptive product that the subject has used per the manufacturer's instructions with every act of sexual intercourse. The subject understands and agrees that during the Day 1 through Month 7 period, she should not have sexual intercourse with males without effective contraception. The use of the rhythm method alone, withdrawal alone, and emergency contraception, are not acceptable methods per the protocol. Subjects who have reached menopause, undergone hysterectomy, bilateral oophorectomy, or bilateral tubal ligation are eligible without the use of contraceptives. Postmenopausal status is defined as: (1) No menses for >1 year but <3 years and confirmed by follicle stimulating hormone (FSH) levels elevated into the postmenopausal range, or (2) no menses for at least 3 years.
5. \* Subject has had no temperature  $\geq 37.8^{\circ}\text{C}$  within 24 hours prior to the first injection.
6. Patient considerations

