### **3.5.5 Statistical Methods**

#### **3.5.5.1 Immunogenicity Analyses**

The primary analyses of immunogenicity will be conducted in the Per Protocol Immunogenicity (PPI) population as defined in Section 3.5.4.1. Immunogenicity data will be analysed separately for HIV and SOT patients. The potential influence of factors such as immunosuppressive therapy and time after transplantation for SOT patients and CD4-count and antiretroviral therapy for HIV patients will be estimated.

- Seroconversion

The primary outcome, seroconversion, defined as changing serostatus from seronegative at Day 1 to seropositive (antibody titre above seroconversion cut-off) by 4 weeks after Dose 3, will be described with 95% CI. Differences with historical controls will be determined with a test for binary (seroconversion or not) proportions.

- GMT

All titers will be log transformed and the antilog of the mean will be calculated to obtain the GMT. GMT will be described with 95%CI. GMTs of immunocompromised patients will be compared with GMTs of historical controls with a one sample *t*-test, comparing month 7 GMTs for each component.

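### Transplant patients aged 18-55 are compared, without age restriction or adjustment, with healthy controls who stop at 45 (or 26), so part of any difference may reflect age

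*Combined protocol and SAP*

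**What the plan says.** - **Patients.** Section 2.3 admits SOT patients "between 18 years and 0 days and 55 years and 365 days for transplant patients at time of signing the ICF", and the SOT hypothesis in section 2.2.1 covers 18-55. HIV patients are enrolled at 18-45.
- **Controls.** For both cohorts, section 2.2.1 names "healthy persons between 18 and 45 years of age" as the preferred historical controls, with "male and female healthy persons between 18 and 26 years of age" as the fallback. For the HIV cohort only, the fallback also includes previous Gardasil data in HIV patients.
- **Availability of controls.** Section 2.1 states of the 9-valent vaccine: "Currently there are no data available for men or women above 26 years of age". It adds that by the end of the trial "data of the V503-004 study which enrolled women between 16 and 45 years of age might be available". The fallback is therefore a real prospect, and the one source mentioned that reaches 45 contains only women.
- **Analysis.** Section 3.5.5.1: "Differences with historical controls will be determined with a test for binary (seroconversion or not) proportions". GMTs are compared by a one-sample t-test.
- **Age in the analysis.** The factors whose influence is to be estimated are examples (immunosuppressive therapy, time after transplantation, CD4 count, antiretroviral therapy), and age is not among them. Section 3.5.5.3 only summarises age descriptively. None of the immunogenicity populations in section 3.5.4.1 has an age criterion.

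**The concern.** Similarity to historical controls is the primary hypothesis, tested for nine HPV types in each cohort. In the SOT cohort the control range ends ten years below the patient range, or 29 years below it under the fallback. If response to the vaccine falls with age in healthy adults, a crude comparison counts that fall against the SOT cohort. The design summary analyses SOT patients separately because it expects immunosuppressive therapy to affect the response more in them, so a reader would naturally put any deficit down to immunosuppression. The planned tests offer no way to tell how much of it is age.

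**Working it through.** **1. The plan's own figure.** Section 3.5.6 gives ±6% for 170 SOT patients at an expected 80%. The Wald half-width is 1.96 × √(p(1−p)/n) = 1.96 × √(0.80 × 0.20/170) = 6.0 points. It reproduces, and this point does not dispute it.

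**2. Overlap of the age ranges** (one-year ages, from sections 2.2.1 and 2.3).

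| Cohort | Ages | Beyond 18-45 controls | Beyond healthy 18-26 controls |
|---|---|---|---|
| SOT | 18-55 (38 years) | 46-55 (10 years) | 27-55 (29 years) |
| HIV | 18-45 (28 years) | none | 27-45 (19 years) |

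The age distribution is not given. If ages were uniform, 10/38 = 26% of SOT patients (about 45 of 170) would be older than every preferred control, and 29/38 = 76% older than every fallback control. The true share above 45 could be well away from 26%, so I also use 20-60%.

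**3. Shift in the pooled SOT rate from age alone.** Shift = share above 45 × assumed fall in seroconversion in those patients.

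| Assumed fall (points) | Share 26% | Share 20-60% |
|---|---|---|
| 0 | 0 | 0 |
| 2 | 0.5 | 0.4-1.2 |
| 5 | 1.3 | 1.0-3.0 |
| 10 | 2.6 | 2.0-6.0 |

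**4. What the test would do with such a shift.** Assume no transplant effect, a fixed control rate, n = 170, 26% above 45, and an exact two-sided one-sample binomial test at 5%. The plan does not name the exact test, and the control rates are assumptions.

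| Assumed fall (points) | Rejects, control rate 99% | Rejects, control rate 95% |
|---|---|---|
| 0 | 3% | 3% |
| 2 | 12% | 5% |
| 5 | 36% | 12% |
| 10 | 74% | 32% |

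With a control rate near 100%, a shift much smaller than ±6 points can be declared a difference. With a small age effect the distortion is slight.

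**5. GMT.** Assume n = 170, an SD of 1.0-1.3 on the natural-log scale, and an age-related titre ratio of 0.7 in 30-50% of patients. The overall ratio is then 0.7^0.3 = 0.90 to 0.7^0.5 = 0.84, and the one-sample t-test rejects in 19-64% of trials with no transplant effect.

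**6. Cost of restricting SOT to age 45 or below.** Uniform ages leave 170 × 28/38 = 125 patients: 1.96 × √(0.16/125) = ±7.0 points. After an assumed 20% loss to per-protocol exclusions, n = 100 gives ±7.8. If 20% to 60% of patients are above 45, n runs from 136 (±6.7) to 68 (±9.5) before exclusions.

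**The case against.** The strongest reply is that the bias is hypothetical. Nothing in the documents shows that seroconversion falls with age, and seroconversion only requires crossing a cutoff. Section 3.5.6 expects 80% in SOT patients; against assumed control rates of 95-99% the anticipated gap is 15-19 points, which a modest age effect would not reverse. The SOT rate with its own interval, on which the study is sized, is unaffected. The list of factors in section 3.5.5.1 is open, so age may be added. All of this stands and limits the weight of the point. It does not remove it: for types where SOT patients respond close to controls, a small shift can decide the test, and an age term fitted within the SOT cohort does not by itself correct a comparison with external controls.

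A reader might also infer that under the fallback most HIV patients have no control of their age. On uniform ages 19/28 = 68% would be older than the healthy 18-26 group. But section 2.2.1 adds previous data in HIV patients to that fallback and gives no age range for them, so the documents do not support a claim that these patients are older than every comparator. Against the preferred controls the HIV age range matches.

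The remedy has limits too. A cut at 45 aligns the upper bound but not the age mix below it, nor sex.

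**Conclusion.** The point holds for the SOT comparison: patients aged 46-55 have no counterpart in any control set, and nothing in the plan restricts or adjusts for age. The size of the bias cannot be derived. The shifts of 0 to 2.6 points rest on an assumed uniform age spread and assumed age effects of 0 to 10 points, so they are scenarios and not estimates. The effect may be near zero for seroconversion and larger for GMT. For the HIV cohort the mismatch arises only under the fallback, and only against its healthy 18-26 comparator.

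A reader might go further and conclude that the trial can say nothing about transplantation, or that a deficit would be mostly age. The documents do not support either: the within-cohort estimate stands, and a deficit of the size planned for would exceed a modest age effect. This is an inexpensive improvement to the primary comparison, not a reason to discard it.

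**What to change.** In section 3.5.5.1, before database lock:

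- Pre-specify that the comparison with 18-45-year-old controls is repeated in SOT patients aged 45 or below, for seroconversion and GMT, and reported beside the all-age result.
- If the 18-26 fallback is used, call the crude comparison with healthy controls descriptive in both cohorts. As supportive results, report the cohort's seroconversion rate and mean log titre estimated at the control ages from a within-cohort regression on age and sex. State that few patients are likely to be that young: on uniform ages 9/38 of 170, about 40 SOT patients.
- If the 18-45 controls turn out to be women only, also report the comparison by sex.

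The cost is SAP wording and extra analyses on data already collected. The restricted set has a wider interval, about ±7.0 points at 80% with 125 patients before per-protocol exclusions and about ±7.8 with 100 after an assumed 20% loss. Fixing the cut in advance matters, because an age limit chosen after the results are seen would carry little weight.
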